### **15.2.3. Serious Adverse Events**

Any SAE experienced by the subject between the time of the first dose of study treatment and the end of the study is to be recorded on the e-CRF and on the SAE Form and faxed or sent by email to Biogen Italia Drug Safety Unit, regardless of the severity of the event or its relationship to study treatment.

Any SAE ongoing when the subject completes the study or discontinues from the study will be followed by the Investigator until the event has resolved, stabilized, or returned to baseline status.

Subjects will be followed for all SAEs until 4 weeks after the last dose of treatment. Thereafter, the event should only be recorded if the Investigator considers it related to study treatment.

### **15.2.4. All Events**

All events must be assessed to determine the following:

- If the event meets the criteria for an SAE as defined in Section 15.1.3.
- The relationship of the event to study treatment as defined in Section 15.3.1.
- The severity of the event as defined in Section 15.3.2.

### **15.2.5. Immediate Reporting of Serious Adverse Events**

In order to adhere to all applicable laws and regulations for reporting an SAE, the study site must formally notify the Biogen Italia Drug Safety Unit within 24 hours of the study site staff becoming aware of the SAE. It is the Investigator's responsibility to ensure that the SAE reporting information and procedures are used and followed appropriately.

### Reporting Information for SAEs

Any Serious Event that occurs between the time that the subject has signed informed consent and the patient final study visit must be reported to the Biogen Italia Drug Safety Unit within 24 hours of the study site staff becoming aware of the event. After 4 weeks after the last dose, **the event should only be recorded if the Investigator considers it related to study treatment.**

A report ***must be submitted*** to Biogen Italia Drug Safety Unit regardless of the following:

- whether or not the subject has undergone study-related procedures
- whether or not subject has received study treatment
- the severity of the event
- the relationship of the event to study treatment

To report initial or follow-up information on a Serious Event, a completed SAE form has to be sent to the following:

Fax: [REDACTED]

Or

e-mail: [REDACTED]

#### 15.2.5.1. Deaths

Death is an outcome of an event. The event that resulted in death should be recorded and reported on the appropriate e-CRF. All causes of death must be reported as SAEs. The Investigator should make every effort to obtain and send death certificates and autopsy reports to Biogen Italia Drug Safety Unit.

### 15.3. Safety Classifications

#### 15.3.1. Relationship of Events to Study Treatment

The following definitions should be considered when evaluating the relationship of AEs and SAEs to the study treatment:

Relationship of Event to commercial drug	
Not related	An adverse event will be considered “not related” to the use of the investigational drug if there is not a possibility that the event has been caused by the product under investigation. Factors pointing toward this assessment include, but are not limited to: the lack of reasonable temporal relationship between administration of the drug and the event, the presence of a biologically implausible relationship between the product and the adverse event (e.g., the event occurred before administration of drug), or the presence of a more likely alternative explanation for the adverse event.
Related	An adverse event will be considered “related” to the use of the investigational drug if there is a possibility that the event may have been caused by the product under investigation. Factors that point toward this assessment include, but are not limited to: a positive rechallenge, a reasonable temporal sequence between administration of the drug and the event, a known response pattern of the suspected drug, improvement following discontinuation or dose reduction, a biologically plausible relationship between the drug and the adverse event, or a lack of an alternative explanation for the adverse event.

### 15.3.2. Severity of Events

The following definitions should be considered when evaluating the severity of AEs and SAEs:

Severity of Event	
Mild	Symptom(s) barely noticeable to subject or does not make subject uncomfortable; does not influence performance or functioning; prescription drug not ordinarily needed for relief of symptom(s) but may be given because of personality of subject.
Moderate	Symptom(s) of a sufficient severity to make subject uncomfortable; performance of daily activity is influenced; subject is able to continue in study; treatment for symptom(s) may be needed.
Severe	Symptom(s) cause severe discomfort; symptoms cause incapacitation or significant impact on subject’s daily life; severity may cause cessation of treatment with study treatment; treatment for symptom(s) may be given and/or subject hospitalized.

### 15.3.3. Expectedness of Events

Like all medicines, Peg-IFN (Plegridy®) can cause side effects, although not everybody gets them. In accordance with the clinical experience of the marketed product, the following events may occur to Peg-IFN (Plegridy®) users:

Serious side effects

- Liver problems
- Depression
- Serious allergic reaction
- Seizures
- Injection site damage
- Kidney problems including scarring that may reduce your kidney function

- Blood problems

- Other side effects (very common side effects, flu-like symptoms, nausea or vomiting, pruritus, hives).

#### **15.4. Prescheduled or Elective Procedures or Routinely Scheduled Treatments**

A prescheduled or elective procedure or a routinely scheduled treatment will not be considered a SAE, even if the subject is hospitalized; the study site must document all of the following:

- The prescheduled or elective procedure or routinely scheduled treatment was scheduled (or was on a waiting list to be scheduled) prior to obtaining the subject's consent to participate in the study.
- The condition requiring the prescheduled or elective procedure or routinely scheduled treatment was present before and did not worsen or progress in the opinion of the Investigator between the subject's consent to participate in the study and the time of the procedure or treatment.
- The prescheduled or elective procedure or routinely scheduled treatment is the sole reason for the intervention or hospital admission.

#### **15.5. Procedures for Handling Special Situations**

##### **15.5.1. Overdose**

An overdose is any dose of study treatment given to a subject or taken by a subject that exceeds the dose described in the protocol. Overdoses are not considered AEs; however, all overdoses should be recorded on the e-CRF and on the Overdose Form and faxed to Biogen Italia Drug Safety Unit within 24 hours, to the number [REDACTED]. The form can be sent to Biogen Idec Italia also via email, to the email address [REDACTED].

An overdose should be reported even if it does not result in an AE.

##### **15.5.2. Medical Emergency**

In a medical emergency requiring immediate attention, study site staff will apply appropriate medical intervention, according to current standards of care. The Investigator or designee should contact the Biogen Italia Medical Director, Drug Safety Unit Responsible, or CRO.

##### **15.5.3. Contraception Requirements**

All subjects of childbearing potential must practice effective contraception during the study and be willing and able to continue contraception for at least 2 weeks after their last dose of study treatment.

For the purposes of this study, women of childbearing potential are defined as all women physiologically capable of becoming pregnant, UNLESS they meet one of the following conditions:

- Postmenopausal: 12 months of natural (spontaneous) amenorrhea or 6 weeks after surgical bilateral oophorectomy with or without hysterectomy.
- Posthysterectomy.

For the purposes of the study, effective contraception is defined as follows:

For females:

- Using 1 or more of the following acceptable methods of contraception: surgical sterilization (e.g., bilateral tubal ligation), intrauterine contraception/device, hormonal contraception, or any 2 barrier methods (a combination of male or female condom with spermicide; diaphragm, sponge, cervical cap).
- Abstinence can be considered an acceptable method of contraception at the discretion of the Investigator. Periodic abstinence (e.g., calendar, ovulation, symptothermal, post-ovulation methods) and withdrawal are not considered acceptable methods of contraception.

For males:

- Effective male contraception includes a vasectomy with negative semen analysis at follow-up, or the use of condoms with spermicide.

#### **15.5.4. Pregnancy**

If a subject (or a male subject's partner) becomes pregnant during the study, she/he must refer it immediately to the Investigator.

If a subject becomes pregnant during the study, the Investigator should stop the treatment and refer to the Plegridy® package insert for further guidance. The Investigator must enter the case of pregnancy in the e-CRF and in the appropriate Form and report it to Biogen Italia Drug Safety Unit, by faxing or e-mailing the appropriate form within 24 hours of the study site staff becoming aware of the pregnancy, at [REDACTED] or [REDACTED]. The Investigator or study site staff must report the outcome of the pregnancy to the Biogen Italia Drug Safety Unit.

Please note that congenital abnormalities/birth defects in the offspring of male or female subjects should be reported when conception occurred during the study treatment period.

#### **15.5.5. Regulatory Reporting**

Suspected Unexpected Serious Adverse Reactions (SUSARs) are SAEs that are unexpected and judged by the Investigator or the Sponsor to be related to the study treatment administered.

Biogen Italia Drug Safety Unit will report SUSARs to the appropriate regulatory authorities and Investigators as required, according to Biogen Idec procedures and to local laws.

### **15.6. Investigator Responsibilities**

The Investigator's responsibilities include the following:

- Monitor and record all AEs, including SAEs and laboratory abnormalities, regardless of the severity or relationship to study treatment and monitor and record all cases of overdose.
- Determine the seriousness, relationship, and severity of each event.
- Determine the onset and resolution dates of each event.
- Monitor and record all pregnancies and follow-up on the outcome of the pregnancy.

- Complete a SAE form for each serious event and send it by fax or email to the Biogen Italia Drug Safety Unit within 24 hours of the study site staff becoming aware of the event.
- Pursue SAE follow-up information actively and persistently. Follow-up information must be reported to the Biogen Italia Drug Safety Unit within 24 hours of the study site staff becoming aware of new information and entered in the e-CRF.
- Ensure all AE and SAE reports are supported by documentation in the subjects' medical records.
- Report SAEs to local ethics committees, as required by local law.

### **15.7. Biogen Italia Responsibilities**

Biogen Italia's responsibilities include the following:

- Before study site activation and subject enrollment, the Clinical Monitor is responsible for reviewing with study site staff the definitions of AE and SAE, as well as the instructions for monitoring, recording, and reporting AEs and SAEs.
- Biogen Italia is to notify all appropriate regulatory authorities, central ethics committees, and Investigators of SAEs, as required by local law, within required time frames.

## **16. STATISTICAL METHODS AND DETERMINATION OF SAMPLE SIZE**

### **16.1. Description of Objectives and Endpoints**

Study objectives and related endpoints are described in Section 6

#### **16.1.1. Primary Objective and Endpoint**

The primary objective of this study is to investigate whether Peg-IFN beta-1a improves the satisfaction of RRMS patients unsatisfied with injectable subcutaneous Interferons, as measured by the Abbreviated Treatment Satisfaction Questionnaire to Medication (TSQM-9), at 12 weeks.

The primary endpoint is to evaluate the changes from baseline in the score of convenience satisfaction domain of TSQM-9 at 12 weeks

#### **16.1.2. Secondary Objectives and Endpoints**

The secondary objectives are:

- to evaluate the effects of Peg-IFN beta-1a treatment on patients' satisfaction at 24 weeks;
- to evaluate the effects of Peg-IFN beta-1a treatment on short-term patients' adherence;
- to evaluate the effects of Peg-IFN beta-1a treatment on patients' fatigue;
- to evaluate the effects of Peg-IFN beta-1a on disease activity and physical disability;
- to evaluate the impact of Peg-IFN beta-1a treatment on patient-reported health-related quality of life;
- to evaluate the impact of Peg-IFN beta-1a treatment on patients' injection-system satisfaction;
- to evaluate the relationship between patients' satisfaction and adherence;
- to evaluate the relationship between patients' satisfaction and social-demographic factors (age, sex, employment working, level of education, etc) and clinical characteristics (ARR, disability, etc.)
- to evaluate the treatment safety and tolerability.

In relation to the primary objectives listed above the following secondary measures will be evaluated:

- Changes from baseline in the score of all domains of TSQM-9 at 24 weeks;
- Changes from baseline in patient adherence to study treatment survey at 12 and 24 weeks;
- Changes from baseline in the score of FSS (Fatigue Status Scale) at 12 and 24 weeks;
- Changes from baseline in the score of Adapted Sclerosis Treatment Concerns Questionnaire (MSTCQ) at 12 and 24 weeks;

- Changes from baseline in the score of Multiple Sclerosis International Quality of Life questionnaire (MusiQoL) at 12 and 24 weeks;
- Changes from baseline in clinical measures (ARR, percentage of relapse-free patients), measures at 24 weeks.
- Incidence and severity of adverse events occurred during the study (including local tolerance to treatment at the injection site).
- Abnormalities in laboratory values.

## **16.2. Demography and Baseline Disease Characteristics**

All the collected data will be summarized at baseline. Continuous variables will be summarized by the mean, standard deviation, median, range and interquartile range. Frequency distributions will be used to summarize categorical variables

## **16.3. Efficacy Data**

### **16.3.1. Analysis Population**

Efficacy population = Full Analysis Set (FAS) consisting of all enrolled patients who took at least one dose of the study medication.

### **16.3.2. General Methods of Analysis**

The primary and secondary endpoints will be evaluated using a repeated measures ANOVA. The repeated measures ANOVA is used to compare group means on a dependent variable across repeated measurements of time. This statistical method is used for making simultaneous comparisons between two or more means of two or more related, not independent, groups.

However, in addition, it could be useful to apply a general linear mixed model that models for group means as fixed effects while simultaneously modeling for individual subject variables as random effects (12).

This kind of model is a subject-specific model and is a choice for analysing longitudinal data.

Unlike the repeated measures ANOVA, which requires a complete balanced array of data, the mixed model can accommodate a dataset with a large portion missing. Although the repeated measures ANOVA requires a fixed time schedule among all individual units, the mixed model can accommodate flexible time schedules. Furthermore, rather than treating time as a categorical variable, as in the repeated measures ANOVA, the mixed model is capable of treating time as either a continuous variable or a categorical variable or both.

Spearman's correlation coefficient measures the strength of association between two ranked variables.

Differences will be considered statistically significant if the p-value will be less or equal to a type I error =0.05 (two-sided test).

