### **16.3.3. Primary Endpoint Analysis**

The primary endpoint (change of TSQM-9 convenience domain at week 12) will be analysed by a repeated measures analysis of variance adjusted for baseline factors (age, sex, disease duration, previous treatment duration, EDSS).

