TSQM Scale scores computed by adding the items loading on each factor. The lowest possible score is subtracted from this composite score and divided by the greatest possible score minus the lowest possible score. This provided a transformed score between 0 and 1 that should be multiplied by 100. (see below) [Note that only one item may be missing from each scale before the subscale should be considered invalid for that respondent]

EFFECTIVENESS

$[(\text{Item 1} + \text{Item 2} + \text{Item 3}) - 3] \text{ divided by } 18) * 100$

If one item is missing

$[(\text{Sum}(\text{Item 1?} + \text{Item 2?} + \text{Item 3?})) - 2] \text{ divided by } 12) * 100$

CONVENIENCE

$[\text{Sum}(\text{Item 9 to Item 11}) - 3] \text{ divided by } 18) * 100$

If one item is missing

$[(\text{Sum}(\text{Item9? to Item11?})) - 2] \text{ divided by } 12) * 100$

GLOBAL SATISFACTION

$[\text{Sum}(\text{Item 12 to Item 14}) - 3] \text{ divided by } 14) * 100$

If either Item 12 or 13 is missing

$[(\text{Sum}(\text{Item12? to Item14?})) - 2] \text{ divided by } 10) * 100$

If Item 14 is missing

$[(\text{Sum}(\text{Item12 and Item13})) - 2] \text{ divided by } 8) * 100$

The TSQM-9 domain scores range from 0 to 100 with higher scores representing higher satisfaction on that domain.

Secondary variables

b) Patients' adherence assessment

A questionnaire assessing adherence and the reasons for not taking drug at the recommended frequency of administration.

c) Patients' Injection-System Satisfaction

- *Adapted Sclerosis Treatment Concerns Questionnaire (MSTCQ)*

The MSTCQ is a validated patient questionnaire developed to address patient concerns with IFN-beta treatment that are not related to efficacy. It has two domains: injection-system satisfaction and side effects. The side-effects domain comprises 3 subscales: ISRs, global side effects, and FLS. All questions in

the MSTCQ have a 5-point response choice, with lower total scores indicating better outcomes. A version adapted for Plegridy will be used.

In scoring of MSTCQ you have a reference to the Scoring manual For Version 3 May 2014.

d) Health Related Quality of Life

- *Multiple Sclerosis International Quality of Life questionnaire (MusiQoL)*

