In addition, routine clinical assessments will be performed in order to check the safety of the Peg-IFN ongoing treatment.

Laboratory Safety Assessments

At the Investigator's discretion, the following routine laboratory tests can be carried out, in order to monitor the safety profile of the ongoing treatment based on Peg-IFN:

- Hematology: RBC- WBC –Haemoglobin- Haematocrit- MCV- MCH – MCHC - Platelets Count – Lymphocytes- Monocytes – Neutrophils – Eosinophils – Basophils
- Blood chemistry: creatinine, blood urea nitrogen (BUN), alkaline phosphatase, ALT, AST, gamma-glutamyl-transferase (GGT).

A pregnancy hCG test (blood sample) will be performed at the baseline visit (T0) to exclude pregnancy, if applicable (it is not required if the subject is post-menopausal or surgically sterilized).

9. Missing data

For missing data in TSQM-9, MSTCQ and MusiQoI see paragraph Variable of analysis.

For the other variables no imputation technique will be apply.

10. Statistical analysis

The primary and secondary endpoints will be evaluated using a repeated measures ANOVA. The repeated measures ANOVA is used to compare group means on a dependent variable across repeated measurements of time. This statistical method is used for making simultaneous comparisons between two or more means of two or more related, not independent, groups.

However, in addition, it could be useful to apply a general linear mixed model that models for group means as fixed effects while simultaneously modeling for individual subject variables as random effects (12). This kind of model is a subject-specific model and is a choice for analysing longitudinal data. Unlike the repeated measures ANOVA, which requires a complete balanced array of data, the mixed model can accommodate a dataset with a large portion missing. Although the repeated measures ANOVA requires a fixed time schedule among all individual units, the mixed model can accommodate flexible time schedules. Furthermore, rather than treating time as a categorical variable, as in the repeated measures ANOVA, the mixed model is capable of treating time as either a continuous variable or a categorical variable or both.

Spearman's correlation coefficient measures the strength of association between two ranked variables.

Differences will be considered statistically significant if the p-value will be less or equal to a type I error =0.05 (two-sided test).

11. Efficacy data

a. Primary Endpoint Analysis

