The primary endpoint is to evaluate the changes from baseline in the score of convenience satisfaction domain of TSQM-9 at 12 weeks. (*Stata instruction: anova var1 time, repeated(time)*)

b. Secondary Endpoints Analysis

- Changes from baseline in the score of all domains of TSQM-9 at 24 weeks;
- Changes from baseline in patient adherence to study treatment survey at 12 and 24 weeks;
- Changes from baseline in the score of FSS (Fatigue Status Scale) at 12 and 24 weeks;
- Changes from baseline in the score of Adapted Sclerosis Treatment Concerns Questionnaire (MSTCQ) at 12 and 24 weeks;
- Changes from baseline in the score of Multiple Sclerosis International Quality of Life questionnaire (MusiQoL) at 12 and 24 weeks;
- Changes from baseline in clinical measures (ARR, percentage of relapse-free patients), measures at 24 weeks.

All the above primary and secondary endpoints will be analysed by a repeated measures analysis of variance adjusted for baseline factors (age, sex, disease duration, previous treatment duration, EDSS) (*Stata instruction: anova var1 var2 time, repeated(time)*).

Correlations between variables will be assessed by a Spearman rank correlation coefficient (*Stata instruction: spearman var1 var2*).

[figure not shown]
To evaluate the relationship between patients' satisfaction and social-demographic factors (age, sex, employment working, level of education, etc.) and clinical characteristics (ARR, disability, etc.) generalized linear mixed models for repeated measurements will be performed (*Stata instruction: mixed var1 var2 || patient:*).

12. Safety Data

a. Adverse events

All events will be coded using the Medical Dictionary for Regulatory Activities (MedDRA). Type and incidence of all AEs will be tabulated. Severity and drug relatedness of all reported AEs will be tabulated.

b. Clinical Laboratory Tests

	Statistical Analysis Plan Protocol N. BIIT0215– Platinum	Pag. 14 di 18
---	---	---------------

For the clinical laboratory data, descriptive statistics will be generated for all tests performed. Laboratory abnormalities will be determined in accordance with the normal ranges of the clinical laboratory. Laboratory abnormalities will be tabulated.

13. Tables

The following tables will be repeated for each visit, if applicable.

- P1. Number and percentage of patients enrolled per center
- P2. Number and percentage of patients stratified by gender; mean and median age, range and interquartile range;

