- P3. Number and percentage of patients stratified by race;
- P4. Number and percentage of patients stratified by educational level;
- P5. Number and percentage of patients stratified by working status;
- P6. Mean and median age, range and interquartile range of time since diagnosis of SM;
- P7. Number and percentage of patients undergoing pharmacological treatment for MS by active substance; mean and median, interquartile range and range of the dose and distribution of the frequency of treatment administration;
- P8. Number and percentage of patients undergoing concomitant pharmacological treatment by active substance; mean and median, interquartile range and range of the duration;
- P9. Mean and median, range and interquartile range of the total number of relapses from the diagnosis;
- P10. Mean and median, interquartile range and range of the total number of relapses in the last year;
- P11. Number and percentage of patients stratified for relevant previous and / or concomitant diseases; if previous, mean and median, range and interquartile range of duration; if ongoing, number and percentage of the diseases being treated;
- P12. Number and percentage of patients stratified by outcome (not performed / normal / abnormal) to physical examination in relation to:
 - a) General appearance;
 - b) Skin;
 - c) Head, neck, thyroid;
 - d) Ear, nose, throat;
 - e) Muscolo-skeletal;
 - f) Respiratory;

- g) Heart;
- h) Peripheral vascular;
- i) Gastrointestinal
- j) Abdomen, liver;
- k) Renal and genitourinary
- l) Endocrine / Metabolic
- m) Neurologic;
- n) Mental status;
- o) Other;

P13. Mean and median, interquartile range and range of height, weight and bmi value

P14. Mean and median, interquartile range and range of temperature, respiration rate, heart rate, maximum and minimum blood pressure;

P15. Mean and median, range and interquartile range of the number of episodes of acute exacerbation since the last visit;

P16. Mean and median, interquartile range and range of EDSS score;

P17. Mean and median, interquartile range and range of TSQM-9, all domains: effectiveness, convenience and global satisfaction;

P18. Change from baseline in the score of convenience satisfaction domain of TSQM-9 at 12 weeks;

P19. Change from baseline in the score of all domains of the TSQM-9 at 24 weeks;

P20. Adjusted repeated measures analysis of variance for change of convenience satisfaction domain of TSQM-9 at 12 and 24 weeks;

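### The primary ANOVA needs complete data by the plan's own account, but no rule covers a missing week-12 score, Early Termination scores are unused, and the time levels are not stated

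*Protocol*

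**What the plan says.** **Endpoint and method.** Protocol 16.3.3: "The primary endpoint (change of TSQM-9 convenience domain at week 12) will be analysed by a repeated measures analysis of variance", adjusted for five baseline factors. SAP 11.a names the same week-12 endpoint. Its printed Stata line, "anova var1 time, repeated(time" (closing brackets omitted here), does not say which visits make up time.

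**Data requirement.** Protocol 16.3.2 and SAP section 10 describe the mixed model by contrast: "Unlike the repeated measures ANOVA, which requires a complete balanced array of data". The mixed model itself is put forward only as an addition: "it could be useful to apply a general linear mixed model".

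**Who is analysed.** The Full Analysis Set needs one dose and no post-baseline score (Protocol 16.3.1, SAP section 5). Protocol 16.5 allows for up to 10% drop-out. Under Protocol 12.1, stopping treatment means leaving the study.

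**Missing data.** SAP section 9: "For missing data in TSQM-9, MSTCQ and MusiQoI see paragraph Variable of analysis". The TSQM-9 text it points to gives an item rule: "only one item may be missing from each scale before the subscale should be considered invalid for that respondent". The statement that nothing will be imputed applies to the other variables.

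**Early Termination.** The schedule in Protocol 4.2 includes TSQM-9 at the ET visit. The SAP gives those scores no role.

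**Tables.** P18 is "Change from baseline in the score of convenience satisfaction domain of TSQM-9 at 12 weeks". P20 is "Adjusted repeated measures analysis of variance for change of convenience satisfaction domain of TSQM-9 at 12 and 24 weeks".

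**The concern.** The plan names a method, says that method needs every cell filled, and plans for cells that will be empty. The TSQM-9 rule declares a subscale invalid when two items are missing and then stops. It does not say what happens to a Full Analysis Set patient who has no week-12 score.

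Two decisions are therefore left until the data are in hand: which patients enter the primary test, and whether week 24 is part of it. If T0, T1 and T2 are all levels and complete data are required, a patient who attended week 12 but left before week 24 can be dropped from a week-12 endpoint. The overall test of time would then also ask whether the mean differs across any of the three visits, which is not a week-12 question.

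Patients unhappy with the new injection may be among those who leave. If they change less favourably than completers, an analysis of completers overstates the gain, and a single-arm study has no control arm to offset this.

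**Working it through.** **Inputs from the documents.** 250 evaluable and 275 enrolled; target change 3 points; SD of change 16; drop-out p up to 10% over the whole 24 weeks (Protocol 16.5). Two-sided 0.05 (Protocol 16.3.2).

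**Assumed, not in the documents.** g = completers' mean change minus drop-outs' mean change, 0 to 5 points; s = share of drop-out that falls before T1.

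1. *The plan's own figure.* Power = Φ(3√N/16 − z). At N = 250, 3√250/16 = 2.965. Two-sided 0.05: Φ(2.965 − 1.960) = 84.2%. One-sided 0.05: Φ(2.965 − 1.645) = 90.7%. The stated 90% returns only with a one-sided test. That is a separate matter; two-sided is used below.

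2. *Precision.* 275 × 0.90 = 247.5. Power is 84.0% at N = 248 and 87.5% at N = 275, a loss of 3.5 percentage points. This is modest.

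3. *Bias of a complete-visit analysis.* If completers change by C and drop-outs by C − g, the mean over all patients is (1 − p)C + p(C − g) = C − pg. The completer mean C is therefore too high by pg.

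| Share lost | g = 0 | g = 5 |
|---|---|---|
| 5% | 0 | 0.25 |
| 10% | 0 | 0.50 |

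4. *Effect on the test.* SE = 16/√247.5 = 1.017. With a true mean change of zero, the chance of a significant improvement is Φ(bias/SE − 1.960). It is 2.5% at zero bias, and Φ(0.492 − 1.960) = 7.1% at a bias of 0.5.

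5. *Using every T0/T1 pair instead.* The remaining bias is g·p·s(1 − p)/(1 − ps). At p = 10% and g = 5:
   - s = 0 (all drop-out after T1): 0
   - s = 0.5: 5 × 0.1 × 0.5 × 0.9/0.95 = 0.24
   - s = 1 (all before T1): 0.5

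   The gain comes from keeping patients who have a week-12 score. It disappears if everyone who leaves does so before week 12.

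6. *ET score where it exists, zero change otherwise.* Take C = 3, g = 5, p = 10%, all drop-out before T1, and assume an ET score reflects the patient's own change (−2). The true mean is 2.5.
   - All have ET scores: 0.9 × 3 + 0.1 × (−2) = 2.5, bias 0
   - Half do: 0.9 × 3 + 0.05 × (−2) = 2.6, bias 0.1
   - None do: 0.9 × 3 = 2.7, bias 0.2

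   If g = 0 and no ET scores exist, the estimate is 2.7 against a true 3.0, so the zero-change rule then errs downward by 0.3.

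7. *Time levels.* With T0 and T1 only, the time test is the week-12 test, and just the missing-score and ET gaps remain. With all three visits, the overall test has two degrees of freedom and is not specific to week 12. The text does not choose between them. P18 points to week 12 alone, while P20 puts both post-baseline visits in one adjusted model.

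**The case against.** **The endpoint is not in doubt.** It is the week-12 change wherever it is stated, and P18 reports it alone. The Stata lines are templates with placeholder variables, and one placeholder stands for five covariates. This stands, and it limits the point to the model's levels and patients.

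**Missing visits were considered.** Both documents raise the mixed model because it tolerates gaps, and P40 tabulates discontinuations with reasons. So it would be wrong to infer that the plan ignores missing data. What is lacking is a role for that model: no trigger, no covariance structure, no primary or sensitivity status.

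**The gaps are assumed.** This also stands. A reader might infer that the primary result will be biased upward. The documents give no drop-out profile; some patients leave for unrelated reasons, and with equal change the bias is zero. A 10-point gap would give 1.0 point of bias and a 16% chance of a false improvement, but it needs the full 10% loss, a gap more than three times the target effect, and no true change.

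**Two further inferences go too far.**
- From P20, that the primary test compares week 24 with week 12. This rests on a table title whose wording recurs for MSTCQ, MusiQoL and FSS (P26, P29, P32), and such a test would answer no stated objective.
- That the primary test would usually be positive with no week-12 effect. With means 0, 0 and 3, N = 250 and a change SD of 16 between every two visits, the noncentrality is 250 × 6/(16²/2) = 11.7 and the overall time test rejects 87% of the time. This needs three levels, no follow-up week-12 contrast, and an effect appearing only at week 24. None of these is confirmed.

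**Conclusion.** The point holds and should be fixed. The stated primary method and the expected data do not fit together, and the text leaves the primary test's patients and time levels open. The documents do not say that incomplete patients will be excluded; exclusion follows only if the plan's own description of its method is applied across all three visits.

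At the planned ceiling of 10% lost, the bias is 0 to 0.5 points for assumed gaps of 0 to 5 points, at most one sixth of the 3-point target. The power cost is about 3.5 percentage points. The missing-score and ET gaps remain whichever time levels were intended; the loss of patients with a usable week-12 score arises only if week 24 is a level.

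**What to change.** **Primary.** State in SAP 11.a that the single primary estimate and test is the week-12 minus baseline contrast, using every Full Analysis Set patient with T0 and T1 scores whether or not T2 exists. The smallest change keeps the adjusted repeated measures ANOVA with T0 and T1 as its only time levels. No centring is needed: main-effect covariates are constant within a patient, so on complete pairs the time contrast is the mean change.

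**Alternative primary.** Give the mixed model that role, with visit as categorical and an unstructured covariance or robust standard errors. It also uses patients with T0 and T2 but no T1, whom the pairs analysis omits. A random patient effect alone, as in the SAP's printed mixed line, is not enough: in simulation the week-12 contrast had a type I error of 5.0%, 6.6% and 7.5% at T1–T2 correlations of 0.5, 0.7 and 0.8 (assumed, with SD 16 and T0 correlations of 0.5).

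**Sensitivity.** Keep the complete-visit ANOVA with its time levels stated. Add one analysis covering every Full Analysis Set patient without a T1 score: the ET TSQM-9 score where it exists, zero change otherwise. Report the number handled each way, including those who missed T1 but attended T2.

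**Cost.** Some added SAP text and code, and no new data, since ET TSQM-9 is already scheduled. The estimate may be less favourable. An ET score can come from early in treatment, so placing it at week 12 is an assumption, as is zero change; that is why this is a sensitivity analysis. The pairs analysis does not remove bias from drop-out before T1.
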